## **8.3 Medical History**

Medical history will be summarized by treatment group for the safety population. Medical history will be coded using the Medical Dictionary for Regulatory Activities (MedDRA), version 18.0, and sorted alphabetically by system organ class and then preferred term by frequency. Subjects with multiple occurrences of the same medical history term will be counted once within the corresponding system organ class and preferred term.

All medical history will be presented in a listing.

## **8.4 Migraine Treatment History**

Migraine treatment history will be summarized by treatment group. The summaries will be presented for the Safety and ITT population. Migraine treatment history will be coded using the

World Health Organization (WHO) Drug Dictionary, version WHODDE 01MAR2015E, and sorted by frequency of preferred name. Subjects with multiple occurrences of the same medication will be counted once within the corresponding preferred name. If the subject has any significant migraine history changes or updates from the parent 301 or 302 study then the new data will be recorded in 305 database. If there are no any changes from previous study and the “New treatment given” is answered as “No” on CRF then migraine history data will be used from parent study for analysis.

All migraine history and migraine characteristics data will be presented in listings.

### **8.5 Characteristics of All Treated Migraine Attacks**

The following will be summarized by treatment group for the mITT and ITT population for all treated migraine attacks in each treatment group. Similar information will also be presented by quarter. Quarter will be defined as time interval of 3 months between each nominal visit number recorded in the database starting from screening visit. E. g. **Screening/Visit 1** to **Month 3/Visit 3** with 3 months duration is Quarter 1.

- Time to dosing from the start of migraine attack (hours)
- Baseline migraine severity
  - Severe (3)
  - Moderate (2)
  - Mild (1)
  - None (0)
- Baseline associated symptoms (yes or no)
  - Nausea
  - Phonophobia
  - Photophobia
  - Vomiting
  - None
- Baseline most bothersome symptom
  - Nausea
  - Phonophobia
  - Photophobia
- Second dose of study drug taken before the 2-hour assessment (yes or no)
- Other medications taken to treat migraine (yes or no)
  - No
  - Yes, before 2-hour assessment
  - Yes, after 2-hour assessment

- Number of treated migraine attacks with second dose
  - Treated as Rescue
  - Treated as Recurrence
  - Missing (if any)
- Total number of treated migraine attacks during entire study
- Average number of migraine attacks treated per 30-day period.

Time to dosing from start of the each treated migraine attack (hours) will be calculated as:  
date/time of dosing –  
date/time of start of the acute migraine attack

Date and time of dosing will be taken from the subject e-diary.

## **9 CONCOMITANT MEDICATIONS**

The frequency and percentage of all concomitant medications use will be presented by treatment group and summarized for the safety population with ATC medication class and WHO drug name. Medications will be coded using the WHO Drug Dictionary, version WHODDEMAR2018 and sorted by frequency of preferred name.

All concomitant medication data will be presented in a listing.

## **10 TREATMENT COMPLIANCE AND EXPOSURE**

Treatment compliance will not be calculated in the study.

Treatment exposure will be assessed in terms of the confirmed dose based on the CRF matched doses with subject's diary entered doses. Based on the matched CRF dosing dates, migraine numbers will be assigned for exposure analysis while still considering the 48 hour interval on the available data. Each treatment will be assigned a number to form a sequence. From the sequence, unique cluster IDs are assigned to treatments if a treatment belongs to an equivalence class of treatments intersecting within 48 hours of each other. Number of treatments will be limited to the maximum number of treatments a subject should have been able to take with respect to the 48 hour rule. This programming process will be used to determine the individual migraine attack. For unmatched CRF dosing dates (e.g. partial dates and dates falling out of visit windows), each reported dose will be counted as a separate migraine attack for safety and exposure analyses. This method will be applied by the programming team for validation purposes. Refer to the analysis dataset specifications for more details.

The number of subjects who have been treated with a first dose for the treatment of at least one migraine during the 0-3 month (Quarter 1) , 3-6 month (Quarter 2), 6-9 month (Quarter 3) and 9-12 month (Quarter 4) time intervals and similarly the number of subjects who have been treated with a second dose for at least 1 migraine during the 0-3 month (Quarter 1) , 3-6 month (Quarter 2), 6-9 month (Quarter 3) and 9-12 month (Quarter 4) time intervals will be reported.

Total number of doses for each subject during the entire study will be calculated based on the number of first and second doses for each treated migraine which will be same as total treated migraine attacks. This data will be calculated for individual subject's CRF confirmed dose data.

Subjects with at least 3 months, at least 6 months (6-Month safety population) and 12 months (12-Month safety population) in the study will be presented with average of  $\geq 2$  treated migraine attacks per month,  $\geq 3$  treated migraine attacks per month and  $\geq 4$  treated migraine attacks per month.

Additionally, for safety population, 3-Month safety population, 6- Month safety population and 12-Month safety population, summary statistics for total number of treated migraine attacks will be tabulated. This data will be presented for n, mean, median, standard deviation, quartiles and minimum and maximum for each treatment group. Total number of treated migraine attacks will also be presented by each quarter as described previously in summary statistics for safety, 6-Month safety and 12-Month safety populations.

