8. STUDY DRUG MATERIALS AND MANAGEMENT

8.1 Study Drug

Study drug refers to lasmiditan 100 mg and lasmiditan 200 mg.

Lasmiditan drug product is a tablet containing 100 mg or 200 mg of lasmiditan (as free base). The tablet is white, film coated, and round with no markings. Lasmiditan drug product is for oral administration.

CCI

Each dose of study drug will consist of one tablet for the treatment of a single migraine attack. For subjects randomized to lasmiditan 100 mg, a second dose may be used for treatment of recurrence of migraine between 2 and 24 hours after the first dose. For subjects randomized to lasmiditan 200 mg, no additional study drug is to be taken within 24 hours of the dose, as the maximum dose of lasmiditan to be taken in a 24-hour period is 200 mg.

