8.5 Administration

Subjects will be screened outside a migraine attack. The study drug will be dispensed to the subject at each visit with instructions to treat all acute migraine attacks as follows:

- **Screening/Visit 1**, subjects will receive a single blister card containing 8 tablets.
- **Month 1/Visit 2** subjects continuing on study may receive a single blister card containing 8 tablets or a patient carton containing two dosing cards of 8 tablets each.
- At each subsequent visit (**Visits 3, 4 and 5/Months 3, 6 and 9**) subjects may receive a single blister card containing 8 tablets or a patient carton containing two dosing cards of 8 tablets each or a patient carton containing 3 dosing cards of 8 tablets each.

Subjects are to return all dosing cards (used and unused to each visit). Additional single dosing cards of 8 tablets are available in the event more study drug is needed to treat migraines during the time between visits or if a subject loses a dosing card or needs a dosing card replaced. Subject use will be monitored to control for medication overuse.

Subjects will be instructed to take one tablet with approximately 4 ounces of water as the FIRST treatment for a new migraine attack providing that: any aura symptoms have resolved

- the headache is either moderate or severe and has been so for less than 4 hours
- no prior analgesic or acute migraine treatment has been taken to treat the current migraine attack.

Subjects will be instructed to take a second dose (one tablet) of study drug (only for those subjects randomized to lasmiditan 100 mg), if needed, with approximately 4 ounces of water for recurrence of migraine at least 2 hours after the first dose. Subjects should not exceed a total dose of 200 mg of lasmiditan in a 24-hour period.

Subjects will be instructed to treat all migraines with lasmiditan as the first treatment for each new migraine attack within 4 hours of onset.

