10.4.3 Treatment Exposure

Treatment exposure will be assessed in terms of the actual dose. Summary statistics will be performed on the number of subjects who took a first dose for the treatment of their migraine and the number of subjects who took both a first and second dose. The average dosage used per month in three month intervals and the cumulative doses taken over the course of the study will be summarized within each treatment arm using descriptive statistics (n, mean, SD, median, minimum, and maximum).

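### SAP 10 equates total doses with treated attacks, limits treatments by an undefined 48-hour rule, and omits the monthly and cumulative dose summaries of Protocol 10.4.3

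*SAP*

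**What the plan says.** - **Protocol 10.4.3.** "Treatment exposure will be assessed in terms of the actual dose". It plans, by arm, descriptive summaries of monthly dosage within three-month intervals and of cumulative doses over the study.
- **Protocol 5.4, 8.1 and 8.5.** Subjects treat all attacks. The dose limit is expressed per 24 hours; for the 200 mg arm, "no additional study drug is to be taken within 24 hours of the dose". Section 8.5 adds: "Subject use will be monitored to control for medication overuse".
- **SAP 10, attacks.** For doses matched between CRF and diary, "unique cluster IDs are assigned to treatments if a treatment belongs to an equivalence class of treatments intersecting within 48 hours of each other". Then "Number of treatments will be limited to the maximum number of treatments a subject should have been able to take", by reference to a 48-hour rule, and "This programming process will be used to determine the individual migraine attack". Where the CRF date is unmatched (partial, or outside the visit window), every reported dose counts as its own attack.
- **SAP 10, doses.** A subject's total doses come from the "number of first and second doses for each treated migraine which will be same as total treated migraine attacks".
- **SAP 10, tables.** Planned are the numbers of subjects with a first dose and with a second dose in each quarter, and counts of treated attacks. No table gives tablets or milligrams, per month or cumulatively.

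**The concern.** The primary objective is the safety of long-term intermittent use, so the amount of drug taken is the context for every safety result. Three features of SAP 10 weaken that information.

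First, the dose total contradicts itself. A sum of first and second doses equals the number of attacks only if nobody takes a second dose or if each dose is called an attack. SAP 6 and SAP 8.5 both plan counts of attacks treated with two doses, so the plan expects them.

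Second, the cap replaces what subjects reported with what they should have been able to take, under a rule that no section defines. The protocol's limit uses 24 hours. The 48-hour periods in the documents are the diary recording period and the treatment-emergence window, and neither restricts dosing.

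Third, the only dose total in SAP 10 is the contradictory one, so the dosage summaries of Protocol 10.4.3 have no counterpart. Protocol 10 says that changes to analysis methods will be described and justified in the SAP. SAP 5.1 lists several changes, but not this one.

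Attack counts matter as well. They decide entry to the 3-, 6- and 12-month safety populations (SAP 4), and treated attacks are the denominator of the per-attack half of the primary endpoint (SAP 12.1).

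**Working it through.** **Plan's own figure.** SAP 4 requires 24 treated attacks for the 12-month safety population: 2 per month × 12 months = 24. It reproduces. The study has no hypothesis-based sample size, so no power calculation applies.

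**1. Doses set equal to attacks.** Let A be attacks and f the share with a second dose. True doses are A(1 + f), reported doses are A, and the share omitted is f/(1 + f). The documents give no f, so these values are assumptions. For A = 24:
- f = 10%: 26.4 doses, 2.4/26.4 = 9.1% omitted
- f = 25%: 30 doses, 6/30 = 20% omitted
- f = 50%: 36 doses, 12/36 = 33.3% omitted

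**2. The cap.** Reading the undefined rule as one treatment per 48 hours, the cap is days × 24/48:
- 30 days: 15 treatments
- 90 days: 45 treatments
- 378 days (maximum time on study): 189 treatments

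One per 24 hours would give 30, 90 and 378. On this reading the cap does not bind for subjects near 2 to 4 attacks per month.

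**3. Chaining.** An equivalence class links neighbouring doses, so a run has no maximum length. Over 30 days:
- every 24 hours: 30 doses, 1 attack
- every 36 hours: 20 doses, 1 attack
- every 49 hours: 15 doses, 15 attacks

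For irregular use, assume Poisson attacks at m per 30 days and drop any dose less than 24 hours after the last one kept. Each gap is then 24 hours plus an exponential time, so the share of treatments falling within 48 hours of the previous one is 1 − exp(−m/30):
- m = 2: 6.5%
- m = 4: 12.5%
- m = 8: 23%

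A simulation of 2,000 subjects per rate over 360 days gave 6.5%, 12.5% and 23.3%.

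**4. Opposite direction.** If all of a subject's dates were unmatched, each dose would count as an attack, and 24 would be reached with 24/(1 + f) true attacks, rounded up:
- f = 10%: 22
- f = 20%: 20
- f = 50%: 16

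**5. What is still reported.** Second doses appear in SAP 6 (attacks with one and with two doses), SAP 8.5 (by rescue or recurrence, and by quarter), SAP 10 (subjects per quarter) and SAP 12.1 (adverse events with one and with two doses). None of these gives monthly dosage or cumulative dose per subject.

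**The case against.** A reader might infer that second doses vanish from the results. They do not, as the last step of the working shows; they are lost only from the dose total.

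A reader might also infer that the cap deletes doses. The text does not say so. The cap sits inside the step that numbers attacks, total doses are specified separately from CRF-confirmed data, and the algorithm's detail is deferred to dataset specifications that are not among these documents. The 48-hour window also has a rationale: response is recorded for 48 hours, and pain returning within that time is recorded as recurrence, so grouping such doses into one attack follows the study's own concept.

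Larger figures are tempting. Without a minimum gap, the Poisson shares would be about 12%, 23% and 41% at 2, 4 and 8 per month. Those include gaps under 24 hours, which break the stated limit in the 200 mg arm and may be second doses of the same attack in the 100 mg arm. A run of ten daily doses recorded as one attack is a constructed extreme, and it compares an attack count with a dose count.

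Nor is the error one-sided. Merging lowers the attack denominator, which tends to raise per-attack adverse event proportions, and it makes the 24-attack threshold harder to reach. By-subject incidence is unaffected. Frequent use remains partly visible through the categories of at least 2, 3 and 4 attacks per month, the maxima and the deviation listing.

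All of this stands. It does not resolve the false equality, the undefined rule or the missing dosage summaries.

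**Conclusion.** The point holds in limited form and should be fixed. The dose total is wrong by construction for every two-dose attack, by f/(1 + f); its size depends on an f that the documents do not supply. The 48-hour rule is undefined and does not match the protocol's 24-hour wording. Chaining can compress frequent dosing in the attack counts, by the shares shown under the Poisson and 24-hour assumptions, while the rule for unmatched dates inflates those counts. The net direction cannot be derived from the documents. The omission of monthly and cumulative dosage is a plain departure from Protocol 10.4.3 that SAP 5.1 does not declare.

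The documents do not support a conclusion that second doses are hidden, that harm is concealed, or that exposure in the study as a whole is understated by half or more. The study is descriptive, and its by-subject safety results do not depend on this section's dose total.

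**What to change.** In SAP 10:
- Delete the clause that makes total doses equal to total treated attacks.
- Define the 48-hour rule, use it only to number attacks, and state that it does not cap doses.
- Restore Protocol 10.4.3: all confirmed doses, uncapped, as first, second and total tablets and milligrams per subject, averaged per month within each three-month interval and cumulatively, by arm.
- Flag or list records closer together than the protocol's stated limit instead of truncating them.
- Reconcile the 48-hour rule with the protocol's 24-hour passages. Which interval is right is not a matter for this review.

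Any part of Protocol 10.4.3 that is deliberately dropped should be listed and justified in SAP 5.1.

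The cost is a wording change and one table from data already held. The downside is that implausible duplicate or retroactive entries, which SAP 5.7 shows are expected, need a query or a flag where the cap would have removed them automatically.

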## **11 EFFICACY ANALYSIS**

This section details the specifications for summarizing efficacy endpoints.

This is an open-label study with no control group. Efficacy data will be summarized using descriptive statistics.

The efficacy endpoints will depend on data collected by e-diary that depends on subject's response entry in the correct order and at the expected scheduled e-diary assessment times. Assessment times are analyzed as calculated by the e-diary and not as part of analysis programming.

### **11.1 Efficacy analysis of secondary endpoint**

For the secondary endpoint the proportion of attacks treated with lasmiditan 100 mg and with lasmiditan 200 mg which respond as headache pain-free at 2 hours will be calculated for each 3 month period based on the treated migraine-level of the mITT population.

The proportion will be calculated as number of attacks which meet the criteria for headache pain-free at 2 hours divided by total number of treated attacks in each treatment group.

This analysis will be presented by treated migraine attack for total no. of attacks in each treatment group. This data will be presented for each three month period of time such as 0 – 3 months after randomization, > 3 – 6 months after randomization, > 6 – 9 months after randomization, > 9 – 12 months after randomization as well as for the entire study.

Headache pain-free is defined as a reduction in headache severity from mild (1), moderate (2), or severe (3) at baseline to none (0).

Treated migraines that do not have a headache pain severity rating at baseline will be excluded from the analysis. Treated migraines that do not have an associated headache pain severity rating at the two-hour time point will be assumed to have not achieved headache pain-free.

Subjects taking any rescue medication within the first two hours will be assumed to have not achieved headache pain-free. Subjects who use other medication prior to the study drug to treat the migraine attack will also be assumed to have not achieved headache pain-free.

Subjects who treat a no (0) severity migraine will not be included in this analysis.

Similar analysis will also be performed for Most Bothersome Symptoms Free at 2 hours post dose and Headache Pain Relief at 2 hours post dose under the same assumptions of sections 11.2.1.2 and 11.2.1.6 .

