7.4 Prohibited Medications

Use of the following medications is prohibited for the duration of a subject's participation in the study from **Screening /Visit 1** through **EoS/ET/Visit 6**:

- Any investigational treatment other than lasmiditan.
- All other symptom modifying treatments (e.g. antiemetics) for migraine except rescue or recurrence medication as detailed in Section 7.3.1 and 7.3.2.
- If a patient requires the initiation of migraine prophylaxis (concomitant medication to reduce the frequency of migraine episodes) or a change in ongoing migraine prophylaxis after the **Screening/Visit 1** they should be withdrawn from the study.

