10.6 Efficacy Analyses

This is an open-label study with no control group. Efficacy data will be summarized using descriptive statistics. The proportion of attacks treated with lasmiditan 100 mg and with lasmiditan 200 mg which respond at 2 hours will be calculated for each 3 month period.

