10.6.1 Headache Response

Headache pain free at 2 hours will be defined as a reduction in headache severity from moderate (2) or severe (3) at baseline to none (0) two hours after dosing with study drug. MBS free at 2 hours will be defined as a 'no' response to the presence of the symptom (either nausea, phonophobia, or photophobia) that was identified as MBS at predose, 2 hours after dosing with study drug.

A qualifying migraine is defined as a migraine treated with study drug within 4 hours of onset

Subjects taking rescue medication within the first two hours or who fail to record headache severity at 2 hours will be assumed to be non-responders in the mITT and the ITT analyses.

A subject is defined to have used rescue medication within the first two hours post dosing if at least one medication is documented in the rescue medication log in the subject electronic diary for which:

$0 \text{ (min)} < \text{date/ time rescue medication (diary)} - \text{date/ time of dosing (diary)} < 120 \text{ (min)}$.

Subjects who do not provide a headache pain severity rating at baseline or who use other medication prior to the study drug for the study migraine attack will be assumed to be non-responders for the mITT and ITT analysis.

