10.6.2 Sensitivity Analyses of the Primary and Key Secondary Endpoints

The analyses of pain free at 2 hours and of MBS free at 2 hours are defined as proportions. The prespecified approach for handling missing data is to assume that subjects with missing data are nonresponders. While this approach is appropriately conservative, a sensitivity analysis will be incorporated to exclude subjects with missing data.

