### **5.1 Changes and Clarifications from the Planned Analysis**

The protocol detailed mITT-2nd Dose and PP-2nd Dose populations. However, the decision was made to run efficacy analyses on the ITT and mITT populations. The populations such as safety-2nd, mITT-2nd Dose and PP-2nd Dose populations were therefore removed. Additionally PP population was removed, as primary endpoint of this study is safety.

The analyses of the primary efficacy measure and other related measures described in the protocol were limited to headaches that were of moderate or severe intensity at the time of dosing. In keeping with subsequent input to CoLucid from the Food & Drug Administration (FDA), the efficacy endpoints will take into account headaches that were of mild intensity at the time of treatment.

The protocol mentioned sensitivity analysis for efficacy endpoints for missing diary data. It was decided not to conduct this analysis, as primary endpoint of this study is safety. The complications of missing efficacy diary data were tested in parent study.

The protocol does not mention an additional subgroup analysis but subgroup analyses described in Section 11.8 will be provided.

Though the protocol did not specify this, it was decided that exploratory analyses would be repeated separately for relief of each associated symptom of headache, including vomiting.

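### With the exclude-missing check dropped, the quarterly 2-hour pain-free table cannot separate a change in response from a change in missing ratings

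*SAP*

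**What the plan says.** The secondary objective (Protocol 5.2) is to explore long-term efficacy as headache response over time. Protocol 10.6 makes the endpoint the proportion of treated attacks "which respond at 2 hours will be calculated for each 3 month period". SAP 11.1 specifies it as attacks that "respond as headache pain-free at 2 hours will be calculated for each 3 month period based on the treated migraine-level of the mITT population", dividing by all treated attacks in the arm.

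Both documents treat a missing 2-hour rating as failure. In Protocol 10.6.1, subjects "who fail to record headache severity at 2 hours will be assumed to be non-responders in the mITT and the ITT analyses". In SAP 11.1, "Treated migraines that do not have an associated headache pain severity rating at the two-hour time point will be assumed to have not achieved" pain-free status.

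Protocol 10.6.2 adds a check on that rule: "While this approach is appropriately conservative, a sensitivity analysis will be incorporated to exclude subjects with missing data". SAP 5.1 withdraws it and gives two reasons. The first is "It was decided not to conduct this analysis, as primary endpoint of this study is safety". The second is "The complications of missing efficacy diary data were tested in parent study".

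**The concern.** The failure rule is the protocol's own and is usually defended as conservative. That defence concerns the level of a single rate. This endpoint is a sequence of four rates, read for whether response holds up. If the share of missing ratings is the same in every quarter, the rule lowers all four rates by the same factor and creates no trend when response is constant. If the share changes, the rule turns a change in diary completion into an apparent change in response.

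Neither reason in SAP 5.1 addresses this. Safety was already the primary objective when the protocol planned the check. Experience with missing diary data in a parent study cannot show how completion behaves over up to 12 months of repeated attacks.

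No test or error rate is affected, since the analysis is descriptive. At stake is any statement that response was maintained, rose or waned over the year, because this table would be its main support.

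**Working it through.** **Do other planned tables show missing 2-hour pain ratings by quarter?**

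- SAP 8.5 (attack characteristics by quarter) covers baseline severity, symptoms, timing and other medication, but has no item for a missing 2-hour rating.
- SAP 10 gives subjects treating and attack counts by quarter, without response or missingness.
- SAP 11.2.1.1 gives pain-free by attack number and by quarter, again counting a missing rating as not pain-free.
- SAP 11.2.1.8 (global impression at 2 hours) is by attack number, not by quarter.
- SAP 11.2.1.2 (most bothersome symptom free) is also given by quarter. It says both that a missing 2-hour symptom rating is a failure and that subjects missing symptoms at a time point are left out there. Its denominators are at best an ambiguous proxy.

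**How far could the planned rate move?** The plan has no figure to reproduce: it states no response, missingness or dropout rate. All inputs below are assumptions: true response p = 34% in every quarter; missing share m = 5% in quarter 1, rising to 8% or 20% in quarter 4; missingness unrelated to response.

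If every attack with a missing 2-hour rating stays in the denominator:

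planned rate = p × (1 − m)

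The first-dose mITT migraine-level definition in SAP 4 is not visible in the text available to me. The visible second-dose recurrence definition requires some post-dose severity or symptom assessment. If the first-dose definition does too, only attacks with an isolated skip at 2 hours remain as failures. With f the share of missing 2-hour ratings that are isolated skips:

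planned rate = p × (1 − m) / (1 − m × (1 − f))

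For example, with f = 0.5 and m = 20%: 34 × 0.80 / (1 − 0.20 × 0.5) = 27.2 / 0.90 = 30.2%.

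| f | m = 5% | m = 8% | Fall | m = 20% | Fall |
|---|---|---|---|---|---|
| 1 (all stay in) | 32.3% | 31.3% | 1.0 | 27.2% | 5.1 |
| 0.5 | 33.1% | 32.6% | 0.5 | 30.2% | 2.9 |
| 0.25 | 33.6% | 33.3% | 0.3 | 32.0% | 1.6 |

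Falls are in percentage points, from unrounded rates. With f = 1 the fall is p × (change in m), so for a rise from 5% to 20% it runs from 0.25 × 15 = 3.8 points at p = 25% to 0.45 × 15 = 6.8 points at p = 45%. An exclude-missing row would show no change in any of these cases. If missingness fell over time, the false trend would be a rise.

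**Would the protocol's check work as written?** It excludes subjects, not attacks. A subject with 24 attacks (2 per month for 12 months) and an independent 5% chance of a missing rating at each has complete data with probability 0.95^24 = 0.29. It would keep only about 29% of such subjects.

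**Is the observed-rating row itself safe?** Not if skipping depends on response. Suppose skipping among attacks that are not pain-free rises from 5% to 20%, and pain-free attacks are skipped half as often:

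- Quarter 1: 0.34 × 0.975 / (0.34 × 0.975 + 0.66 × 0.95) = 0.3315 / 0.9585 = 34.6%.
- Quarter 4: 0.34 × 0.90 / (0.34 × 0.90 + 0.66 × 0.80) = 0.306 / 0.834 = 36.7%.

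With f = 1, the planned row falls from 33.15% to 30.6% in the same case (the two numerators). The rows move in opposite directions while true response is constant.

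**The case against.** The strongest defence has four parts.

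*The change is legitimate.* SAP 5.1 discloses it with reasons, and Protocol 10 allows changes to non-principal analysis methods to be described in the SAP. This stands: it is not a concealed departure. The issue is whether the reasons fit the use made of the table.

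*Missingness may not drift.* Protocol 6.2 excludes rollover subjects judged noncompliant with the diary, compliance is reviewed at each visit, the diary sounds alarms, and SAP 5.7 removes doses recorded only on the CRF from the efficacy analysis. These safeguards make a large rise less likely, and nothing in the documents supports 20% in particular. They do not rule out drift. SAP 5 opens the questions only within 5 or 10 minutes of each time point, and a late diary start forfeits time points already passed, so isolated gaps are possible.

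*The protocol's check was not built for this.* It is written for pain-free and symptom-free at 2 hours in general, does not mention quarters, and excludes whole subjects. This also stands, so an attack-level row replaces that check; it does not reinstate it.

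*Who is left.* A reader might infer that dropping the check also leaves selective dropout unexamined, and that the quarterly trend is therefore uninterpretable. The documents do not support that. Pooling whoever is still treating in each period comes from Protocol 10.6, and excluding missing ratings would never have addressed it. Composition can change: under Protocol 7.4, "If a patient requires the initiation of migraine prophylaxis (concomitant medication to reduce the frequency of migraine episodes") or a change in it leads to withdrawal, and the direction of any effect on the rate is unknown. But SAP 11.2.1.1 plans a same-subject comparison: for subjects with 5 or more treated migraines, 2-hour pain-free over the first five and per-subject response over all attacks. If each subject's response and the missing share are constant, the two should agree whoever drops out later. The table is not by quarter, its overall figure includes the first five attacks, and it too counts a missing rating against response. It answers the dropout question in part and the missing-rating question not at all.

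**Conclusion.** The concern holds for missing ratings. SAP 11.1 counts them as failures, SAP 5.1 removes the only planned check on that rule, and no planned table is specified to show by quarter how many there are. A change in missingness could be read as a change in response.

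The size is unknown. Under the assumed 34% response and missing ratings rising from 5% to 8–20%, the false fall is 1.0 to 5.1 points, or 0.3 to 2.9 points on the narrower reading of the mITT attack population with a quarter to a half isolated skips. These are illustrations, not estimates, and they assume missingness unrelated to response.

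The effect is on interpretation of a descriptive secondary endpoint. The documents do not support a claim that the planned rates are biased in a known direction. This is worth changing because it is cheap, not because the analysis is invalid.

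**What to change.** Keep the planned row as the main analysis. In the SAP 11.1 table, by quarter and arm:

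1. Print the number and percentage of attacks with a missing 2-hour severity rating.
2. Add an attack-level row excluding those attacks, and say in SAP 5.1 that it replaces the protocol's subject-level exclusion.

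The cost is a little more programming on data already collected. The statistical downside is the one shown above: the observed-rating row is biased if skipping depends on response, so it should be read only beside the planned row and the missing counts.

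Two optional additions. A quarterly row in the same subjects (those treating at least one attack in all four quarters) would help with dropout, if labelled as describing only those who stayed. One definition of quarter would also be tidier: SAP 11.1 counts from randomization, while SAP 11.2.1.1 uses the nominal-visit quarters of SAP 8.5. Under the protocol's visit windows, boundaries can slip by at most 2 + 4 = 6, then 10, then 14 days at Visits 3, 4 and 5, so this is housekeeping.
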